4.4 Premature Termination of the Study

This study could be terminated prematurely by the sponsor (i.e.due to finance or administrative reasons et al), regulatory authority, or the ethics committees from the perspective of protecting the subjects' rights and interests. In case of premature termination of the study, no subjects would be enrolled, the database will be closed after 90 days assessment of the last enrolled patient and results will be reported.

5 Randomization and Treatment allocation

Subjects will be randomized via an Internet-based randomization system in a 1:1 manner to treatment with BGCs(Intervention group) or not(control group), stratified by site, preferred initial thrombectomy strategy(stent retriever VS aspiration VS stent retriever + aspiration), and onset to randomization time(<6 hours VS \geq 6 hours). The randomization sequence will use a minimization algorithm to ensure balance in key prognostic factors. Randomization is allowed when large vessel occlusion has been established.

Subjects will be treated with thrombectomy based on the results of randomization.

Intervention group: Subjects treated with BGCs combined with conventional thrombectomy.

Control group: Subjects treated with standard guide catheter combined with conventional thrombectomy.

Any National Medical Products Administration (NMPA) devices (including the use of a thrombectomy stent, distal aspiration catheter, or combine use of both) are allowed.

6 Study Method

6.1 Study Outcomes

6.1.1 Primary Outcomes

The primary outcome is functional outcome, defined as modified Rankin Scale (mRS) score shift at 90 days (±14 days).

The modified Rankin Scale (mRS) is an ordinal hierarchical scale ranging from 0 to 5, with higher scores indicating more severe disability. A score of 6 has been added to signify death.:

0 = No symptoms;

1 = Symptoms, no disability: Minor symptoms that do not interfere with lifestyle;

15 / 43

- 2 = Slight disability: Slight disability, symptoms that lead to some restriction in lifestyle, but do not interfere with the patient's capacity to look after himself.;
- 3 = Moderate disability: Moderate disability, symptoms that significantly restrict lifestyle and prevent totally independent existence;
- 4 = Moderately severe disability: Moderately severe disability, symptoms that clearly prevent independent existence though not needing constant attention;
- 5 = Severe disability, totally dependent patient requiring constant attention day and night.
- 6 = Death.

6.1.2 Secondary Outcomes

- Dichotomized mRS at 90 days after the procedure (0-1 versus 2-6, 0-2 versus 3-6,0-3 versus 4-6, 0-4 versus 5-6, 0-5 versus 6);
- Change in stroke severity (NIHSS score, the criteria for scoring are detailed in Appendix 1) at 24 hours post treatment;
- Change in stroke severity (NIHSS score) at 7 days post treatment or discharge (whichever occurs first);
- 4) Final infarction volume at 5-7 days post treatment;
- 5) Technical success rate (defined as successfully navigating the guide catheter into the target vessel, and finishing the mechanical thrombectomy procedure without changing to another guide catheter);
- Reperfusion outcome (eTICI 2b or greater, eTICI 2c or greater, eTICI 3; eTICI criteria are detailed in Appendix 2) in final angiogram;
- Reperfusion outcome (eTICI 2b or greater, eTICI 2c or greater, eTICI 3) after the first pass;
- Time from groin puncture to successful reperfusion (eTICI 2b or greater, eTICI 2c or greater);
- Percentage of subjects with acceptable revascularization quality (eTICI 2b or greater, eTICI 2c or greater) within 45 min of access;
- 10) Number of thrombectomy attempts (final);

11) Occurrence of emboli to a new territory.

6.1.3 Safety Outcomes

- 1) Deaths at 90 days (± 14 days) post treatment;
- 2) Intracranial hemorrhage, symptomatic intracranial hemorrhage or asymptomatic intracranial hemorrhage at 7 days post treatment or discharge (whichever occurs first);
- 3) Other serious adverse events (SAEs) adjudicated by the Clinical Events Committee;
- 4) Any peri-procedural complications, including vessel dissection, arterial perforation, and femoral access complications, etc.

6.1.4 Cost Outcomes

- 1) Health-related quality of life using EQ-5D (see Appendix 3);
- 2) Utility-weighted mRS scores;
- 3) Duration of hospitalization;
- 4) Treatment cost.

6.1.5 Blinding

Both patient and treating physician will be aware of the treatment assignment. But outcome evaluation would be blinded. Information on outcome at 90 days will be assessed through standardized forms and procedures, by a trained investigator blinded for treatment allocation. Interviews will be recorded. Assessors who are blinded to the treatment allocation will perform assessment of outcome on the modified Rankin scale on this information. Results of neuro-imaging will be also assessed in a blinded manner. Information on treatment allocation will be kept separate from the main study database. The steering committee will be kept unaware of the results of interim analyses of efficacy and safety. An independent DSMB statistician will combine data on treatment allocation with the clinical data in order to report to the data monitoring committee (DSMB).

6.2 Study Procedures

6.2.1 Schedule of Study Activities

PRØIECT-MT

The study procedure is shown in the table below.

Procedure/Time Window	Baseline	1 day post treatment	7 days post treatment [#]	90 days post treatment	
	Pre-operation - the day of treatment*	±12 hours	±2 days	±14 days	
Informed consent	Х				
Demographics ¹	X				
Medical history ²	X				
Vital signs ³	Х	Х	Х		
Blood routine test ⁴	Х	Х			
Blood biochemistry ⁵	Х	Х			
Coagulation function test ⁶	Х	Х			
Imaging examination ⁷	Х	Х	Х		
mRS score ⁸	Х			Х	
GCS score ⁹	Х	Х	Х		
NIHSS score ¹⁰	Х	Х	Х		
Quality of life using EQ- 5D ¹¹				Х	
Inclusion/exclusion criteria evaluation ¹²	Х				
Randomization and thrombectomy treatment ¹³	Х				
Medical cost			Х	Х	
Safety evaluation ¹⁴	Х	Х	Х	Х	
Concomitant medication ¹⁵	Х	Х	Х	X	

Notes: #: at discharge or 7 days post treatment, whichever occurs first. *: The end date of surgery will be considered as the day of surgery.

- 1. **Demographics:** Age, sex, height and weight;
- 2. **Medical history:** Including medical history of stroke, carotid artery disease, cardiac disorders, peripheral arterial disease, hypertension, diabetes mellitus, and hypercholesterolaemia et al, stroke risk factors including history of smoking, alcohol drinking etc, and history of allergy (allergen);
- 3. Vital signs: Pulse, blood pressure, respiration rate, and body temperature;
- 4. **Blood routine:** Red blood cells (RBC) count, white blood cells (WBC) count, neutrophils count, lymphocytes count, monocytes count, platelets (PLT) count, and hemoglobin (HGB);
- 5. Blood biochemistry: Creatinine (Cr), blood urea or blood urea nitrogen (Urea/BUN), and glucose (Glu);
- 6. **Coagulation function:** Prothrombin time (PT), activated partial thromboplastin time (APTT), and international normalized ratio (INR);

- 7. **Imaging examination:** Data of brain imaging examinations (such as CT/CTA, MRI/MRA or DSA) performed at each visit will be collected;
- 8. **mRS score:** mRS score of subjects before this onset and mRS score at 90 days post treatment will be collected;
- 9. GCS score: GCS scores immediately before randomization, and at 1 day and 7 days post treatment will be collected;
- 10. **NIHSS score:** NIHSS scores immediately before randomization, and at 1 day and 7 days post treatment will be collected;
- 11. Quality of life using EQ-5D: EQ-5D quality of life score at 90 days post treatment will be collected.
- 12. Inclusion/exclusion criteria evaluation: Subjects will be evaluated for eligibility using the inclusion and exclusion criteria after signing the informed consent form, to determine whether they can be randomized;
- 13. **Randomization and thrombectomy treatment:** Subjects will be randomized to the intervention group and the control group at the ratio 1:1 after confirming the eligibility, and receive thrombectomy treatment in the intervention group or control group according to the result of randomization. Information related to thrombectomy treatment will be collected and recorded, which include but not limited to: information of product used for embolectomy, technical success rate, reperfusion outcome in final angiogram and after the first pass, time from femoral artery puncture to successful reperfusion, revascularization quality within 45 minutes, mechanical embolectomy attempts (final), and occurrence of emboli to a new territory, etc.;
- 14. **Safety evaluation:** All-cause death, intracranial hemorrhage, other SAEs, and procedure-related complications during the study will be collected;
- 15. **Concomitant medication:** including thrombolytics, anticoagulants, antiplatelets, blood pressure/lipid and blood glucose control medications taken by the subjects during the study, and concomitant medications associated with any SAE.

6.2.2 Study Visits

The study consists of a total of 4 visits, including: Visits at baseline (pre-procedure~ the day of treatment), 1 day (\pm 12 hours) post treatment, 7 days (\pm 2 days) post treatment or at discharge, and 90 days (\pm 14 days) post treatment.

6.2.2.1 Visit 1: Baseline Visit (Pre-operation to the Day of Treatment)

At baseline, subjects will firstly be screened for the study. Each site should keep log of all AIS patients with LVO confirmed by brain imaging arriving <24 hours of symptom onset (or last known well) and who were considered for the study but subsequently excluded. The screening log will record patients' initials and date of admission together with a brief description of the

main reason as to why a patient was not randomized. The log will be used by the Research Coordinator, PI and the CCC to monitor recruitment and to identify specific barriers to randomisation of eligible patients. The investigator should introduce the potential subjects or approved surrogates about the purpose of the study and the contents in the informed consent form (ICF). Data collection would begin only when both the subject or his/her surrogate and the investigator have signed and dated on the ICF.

The following information will be collected for subjects at this visit:

- 1) Date of signature on ICF.
- 2) **Demographics**: Age, sex, height and weight.
- Medical history: Including medical history of stroke, carotid artery disease, cardiac disorders, hypertension, diabetes mellitus, and hypercholesterolaemia et al, stroke risk factors including history of smoking, alcohol drinking etc, and history of allergy (allergen).
- 4) Vital signs: Pulse, blood pressure, respiration rate, and body temperature.
- 5) Laboratory tests:
 - a) Blood routine: Red blood cells (RBC) count, white blood cells (WBC) count, neutrophils count, lymphocytes count, monocytes count, platelets (PLT) count, and hemoglobin (HGB).
 - b) Blood biochemistry: Creatinine (Cr), blood urea or blood urea nitrogen (Urea/BUN), and glucose (Glu).
 - c) Coagulation function: Prothrombin time (PT), activated partial thromboplastin time (APTT), and international normalized ratio (INR).
- Imaging examination: Data of brain imaging examinations (such as CT/CTA, MRI/MRA or DSA) performed at this visit will be collected.
- 7) **mRS score:** mRS score of the subjects before this onset will be collected.
- 8) Glasgow Coma Scale (GCS) score: GCS score immediately before randomization will be collected.
- 9) **NIHSS score:** NIHSS score immediately before randomization will be collected.

- 10) **Inclusion/exclusion criteria evaluation:** Eligibility of the subjects will be evaluated according to the inclusion and exclusion criteria after obtaining signed informed consent form, to determine whether they can be randomized.
- 11) Randomization and thrombectomy treatment: subjects will be randomized via an Internet-based randomization system in a 1:1 manner to treatment with BGCs(Intervention group) or not(control group), stratified by site, preferred thrombectomy strategy(stent retriever VS aspiration VS stent retriever + aspiration), and onset to randomization time(<6 hours VS \geq 6 hours)

Information related to thrombectomy procedure will be collected and recorded, which include but not limited to: Information of product used for thrombectomy, technical success rate, reperfusion outcome in final angiogram and after the first pass, time from femoral artery puncture to successful reperfusion, revascularization quality within 45 minutes, thrombectomy attempts (final), and occurrence of emboli to a new territory, etc.

- 12) **Safety evaluation:** All-cause death, intracranial hemorrhage, other SAEs, and procedure or device related complications experienced by subjects during the study will be collected.
- 13) **Concomitant medication:** Thrombolytics, anticoagulants, antiplatelets, blood pressure/lipid and blood glucose control medications taken by the subjects during the study, and concomitant medications associated with any SAE will be collected.

6.2.2.2 Visit 2: 1 day (±12 hours) post treatment

The following information will be collected from the subjects at this visit:

- 1) Vital signs: Pulse, blood pressure, respiration rate, and body temperature;
- 2) Laboratory tests:
 - a) Blood routine: Red blood cells (RBC) count, white blood cells (WBC) count, neutrophils count, lymphocytes count, monocytes count, platelets (PLT) count, and hemoglobin (HGB);
 - b) Blood biochemistry: Creatinine (Cr), blood urea or blood urea nitrogen (Urea/BUN), and glucose (Glu);

PRØIECT-MT

- c) Coagulation function: Prothrombin time (PT), activated partial thromboplastin time (APTT), and international normalized ratio (INR);
- 3) Imaging examination: results of imaging examinations such as CT scan will be collected;
- 4) GCS score;
- 5) NIHSS score;
- 6) Safety evaluation: All-cause death, intracranial hemorrhage, other SAEs, and procedurerelated complications experienced by subjects during the study will be collected;
- 7) Concomitant medication: Thrombolytics, anticoagulants, antiplatelets, blood pressure/lipid and blood glucose control medications taken by the subjects during the study, and concomitant medications associated with any SAE will be collected.

6.2.2.3 Visit 3: 7 days (±2 hours) post treatment or at Discharge

The following information will be collected for subjects at this visit:

- 1) Vital signs: Pulse, blood pressure, respiration rate, and body temperature;
- 2) GCS score;
- 3) NIHSS score;
- 4) Imaging examination: Data of imaging examinations such as CT scan will be collected;
- 5) Medical cost;
- 6) Safety evaluation: All-cause death, intracranial hemorrhage, other SAEs, and procedurerelated complications experienced by subjects during the study will be collected;
- 7) Concomitant medication: Thrombolytics, anticoagulants, antiplatelets, blood pressure/lipid and blood glucose control medications taken by the subjects during the study, and concomitant medications associated with any SAE will be collected.

6.2.2.4 Visit 4: 90 days (±14 days) post treatment

- 1) mRS;
- 2) Quality of life evaluation using EQ-5D;
- 3) Medical cost;

- Safety evaluation: All-cause death, intracranial hemorrhage, other SAEs, and procedurerelated complications experienced by subjects during the study will be collected;
- 5) Concomitant medication: Thrombolytics, anticoagulants, antiplatelets, blood pressure/lipid and blood glucose control medications taken by the subjects during the study, and concomitant medications associated with any SAE will be collected.

7 Statistical Analysis

7.1 Sample Size

In a meta-analysis comparing BGC with standard guide catheter, the use of balloon guide catheter improved the proportion of functional outcome by $10.8\%^{[22]}$. In this study, based on a more conservative estimate, we assume the usage of BGC would improve the function outcome by 8%.

Based on the distribution of the mRS in the control group of the trial, which we derived from the intervention group of the MR CLEAN trial: mRS0: 3%; mRS 1: 9%; mRS 2: 21%; mRS 3: 18%; mRS 4: 22%; mRS 5: 6% and mRS 6:21%. We assumed a favorable treatment effect with a common odds ratio (cOR) of 1.43, corresponding to an 8% absolute increase in the rate of mRS scores of 0-2. In a simulation with 5000 runs we computed the proportion of positive trials, for a given sample size. A sample size of 1074 subjects is estimated to be able to demonstrate this treatment effect with 87% power and 5% type-1 error. This sample size also allows for 5% dropout rate and 5% crossover rate.

7.2 Methods for Statistical Analysis

Analyses will be performed based on the intention-to-treat (ITT) principle. Baseline data by treatment allocation will be reported with statistical procedures. Missing values for baseline

characteristics will be reported. Missing baseline characteristics will be imputed using regression imputation as appropriate. The primary outcome will be analyzed by means of an ordinal logistic regression. Pre-defined subgroups will be analyzed by testing for interaction between the specific baseline characteristic and treatment. Any reported SAE or discontinuation of assigned treatment due to an SAE will be classified using MedDRA.

Statistical analyses will be detailed in the pre-specified Statistical Analysis Plan (SAP).

The study consists of 2 interim analyses to be performed when 30% and 60% of the 90-day follow- up data have been collected. The independent data and safety monitoring board (DSMB) will adopt the Haybittle-Peto rule, and $\alpha < 0.001$ in the interim analysis will be considered as statistically significant. Because only 2 interim analyses will be performed, the conventional significance level ($\alpha = 0.0482$) will be used for final analysis. The DSMB will monitor SAEs (e.g. death, spontaneous intracerebral hemorrhage [sICH], and neurological deterioration) periodically, and the occurrence of excessive SAEs will trigger discussion regarding termination of the study.

8 Study Monitoring

Qualified Clinical Research Associates (CRAs) will be responsible for regular monitoring of this study according to the monitoring plan. The monitoring is to ensure that all parties involved in the clinical study comply with the requirements in the Good Clinical Practice (ICH-GCP/GCP) and other applicable regulations during the implementation of the study, to protect the rights of the subjects and ensure the compliance with the clinical study protocol/procedures, as well as the authenticity, completeness and accuracy of the collected data.

Monitoring procedures include one or more visits before study initiation, regular monitoring visits during the study according to the agreed frequency of monitoring, and monitoring visits related to site closure after the end of the study.

9 Data Management

9.1 Data Collection

Electronic data capture (EDC) system will be used in this study, collected data will be entered into the electronic case report form (eCRF) by the investigator or authorized staff, who will receive extensive training prior to data entry. Measures will be taken to ensure the information security.

The investigators are responsible for maintaining all original documents. A complete eCRF for each enrolled subject, regardless of the duration of his/her participation, should be submitted

by the investigators or authorized staff. All supporting documents (e.g., laboratory records or records of various clinical research organizations) submitted with the eCRF would be marked with study number, all personal privacy information (including subject names) would be confidential to protect the privacy of the subjects.

9.2 Data Entry and amendment

Investigators and authorized staff would be responsible for data entries, corrections and amendments. Any change to the data will be documented, i.e. reason for change, name of operator, and the time and date of change should be documented. Any correction to the data in the eCRF should signed by the investigators. When there was doubt about the collected data, CRA or data management personnel will raise the query in the EDC system, it is the responsibility of the investigators to answer the query. The EDC system will document the audit trail, including the investigator's name, time and date of the query.

9.3 Lock of Database

After verified by the data management personnel, principal investigator (PI), statistician, and study monitoring personnel, the data administrators will lock the database. Generally, the locked database should not be changed.

9.4 Transfer of Database

The locked database will be transferred to statistician for statistical analysis according to statistical analysis plan, who will develop the statistical analysis report after completing the statistical analysis.

10 Adverse Events/Serious Adverse Events

10.1 Adverse Events (AEs)

10.1.1 Definition of Adverse Events

Adverse events (AE) are any untoward medical occurrence in the clinical investigation, whether or not considered to be related to the device / procedure.

10.1.2 Classification of Adverse Events

1) Classification by the severity of AE

The course, severity, treatment and outcome of AEs should be monitored carefully and recorded in the AE reporting form. The severity of an AE can be classified as mild, moderate, or severe according to the following criteria.

Severity	Description						
Mild	Transient or mild discomfort, with no limitation of activity, and no medical intervention/treatment required.						
Moderate	Obvious limitation of activity, often requiring assistance, medical intervention/treatment, and hospitalization may be necessary.						
Severe	Extreme limitation of activity, requiring significant assistance and significant medical intervention/treatment, and requiring hospitalization or probabl requiring hospice care.						

Table 10-1	Adverse	Events	hv	Severity
1abic 10-1	nuverse	Livenes	vy	Severity

2) Classification by relationship of AE to the study device/procedure:

For all collected AEs, the relationship of the AE to the study device or procedure will be determined by the investigator based on temporal relationship and his/her clinical judgment. The following categories will be used for grading relevance.

Criteria for a causal relationship of AE and the Study Device or Procedure:

- 1) AE follows a fair temporal sequence from the study device or procedure;
- 2) The event is a known effect of the study device or the procedure, or a possible effect can be explained by the mechanism of the study device or the procedure;
- 3) The event relieves or ceases after stopping use of the device or procedure;
- 4) The event reappears after reuse of the device or procedure;
- 5) The event could not be explained by other contributing factors.

Any event meeting five items of the criteria above will be considered as "definitely related"; while any event meeting two of the criteria above will be considered as "possibly related".

Criteria for a relationship unrelated to the Study Device or Procedure:

- 1) AE follows a fair temporal sequence from the study device or procedure ;
- This type of adverse events is impossible to be caused by the study device or surgical procedure;

 The adverse event can be explained by the concomitant use of other device/drug, subject's disease progression, or other treatment effects.

Any event meeting three items of the criteria above will be considered as "definitely unrelated"; while any event meeting one of the criteria above will be considered as "unlikely related".

Among which, events whose causal relationship is judged as definitely related or possibly related will be considered as related to the study device or procedure.

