2.1.3 Safety

2.1.3.1 Adverse events (AEs)

This study focused on the SAEs and peri-procedural complications adjudicated by the Clinical Events Committee.

All SAEs terms will be coded using MedDRA 25.0 or higher before study database lock. MedDRA System Organ Class (SOC) and Preferred Term (PT) will be presented in the summary tables.

Definition of SAEs

Any SAEs that occurs during the study will be recorded by the investigator from the time that the study treatment is started for the subject. According to the WHO International Centre for Drug Monitoring (1994), SAEs is defined as any of the following untoward medical events which:

- 1) Results in death;
- 2) Is life threatening in the view of the principal investigator (i.e. its occurrence places the patient or subject at immediate risk of death. It does not include an adverse event, had it occurred in a more severe form, might have caused death);
- 3) Requires inpatient hospitalization or prolongation of existing hospitalization;
- 4) Results in a persistent or significant disability or incapacity;
- 5) Result in congenital anomaly or birth defects;
- 6) Important medical events that may not result in death, be life-threatening, or require hospitalizations but may jeopardize the subject and may require medical or surgical intervention to prevent one of the outcomes listed above according to the principal investigator.

Classification by relationship of SAEs to the study device/procedure

Relationship between SAEs and study device/procedure, the investigator will evaluate the possible association between adverse events and study device/procedure according to the time relationship and its clinical judgment in terms of "definitely related", "possibly related", "definitely unrelated", "unlikely related" and "unable to determine". Among which, events whose causal relationship is judged as "definitely related" or "possibly related" will be considered as related to the study device or procedure. If a relationship to the study device or procedure was missing, the analysis was considered to be related to the study device or procedure when appropriate.

Definition of peri-procedural complications

Peri-procedural complications for this study refers to complications at time of discharge or 7 days post-randomization, which include procedural complications, procedure related complications, etc., such as vessel dissection, arterial perforation, and femoral access complications.

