Classification by relationship of peri-procedural complications to the study device/procedure

Relationship between peri-procedural complications and study device/procedure, the investigator will evaluate the possible association between adverse events and study device/procedure according to the time relationship and its clinical judgment in terms of "definitely related", "possibly related", "definitely unrelated", "unlikely related" and "unable to determine". Among which, events whose causal relationship is judged as "definitely related" or "possibly related" will be considered as related to the study device or procedure. If a relationship to the study device or procedure was missing,

the analysis was considered to be related to the study device or procedure when appropriate.

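### In Protocol 10.1.2 the unrelated criteria open with the same un-negated time-link item as the related criteria, so a time link counts towards an unrelated grade

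*Protocol*

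**What the plan says.** Protocol 10.1.2 asks the investigator to grade the relationship of every collected adverse event to the study device or procedure.

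- **Related list, five items.** In short: a time link; a known or mechanistically plausible effect; relief on stopping; return on reuse; no other explanation. Item 1 reads "AE follows a fair temporal sequence from the study device or procedure". Five items give *definitely related*; for the lower grade the rule is "while any event meeting two of the criteria above will be considered as" *possibly related*.
- **Unrelated list, three items.** Item 1 is the same sentence, with no negation. Items 2 and 3 are that the device or procedure cannot cause this type of event, and that something else explains it. The rules are "Any event meeting three items of the criteria above will be considered as" *definitely unrelated* and "while any event meeting one of the criteria above will be considered as" *unlikely related*.
- **Pooling.** The Protocol then states that "events whose causal relationship is judged as definitely related or possibly related will be considered as related to the study device or procedure".

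SAP 2.1.3.1 repeats the grades for SAEs and, under "Classification by relationship of peri-procedural complications to the study device/procedure", for complications. It gives no item counts, adds a fifth grade (*unable to determine*), and counts a missing relationship as related where appropriate.

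**The concern.** A list meant to identify unrelated events should not open with the main sign of relatedness. With the same sentence on both lists, every event that has a time link starts with one of the three unrelated items already met, which is enough for *unlikely related*. Absence of a time link, normally an argument against causation, earns nothing on the unrelated list.

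At stake is whether the investigators at the planned 40-60 sites (Protocol 13.2) grade alike when they apply the written criteria. Treating physicians know the allocation (Protocol 6.1.5), so clear criteria are worth having.

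**Working it through.** The plan gives no figure to reproduce. The check is to apply its own thresholds.

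**Inputs (Protocol 10.1.2).** Call the related items R1 to R5 and the unrelated items U1 to U3, each scored 1 if met and 0 if not. Related score = R1+R2+R3+R4+R5. Unrelated score = U1+U2+U3. As written, U1 = R1. If item 1 meant the absence of a time link, U1 would be 1 − R1.

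| Event | Related score | Unrelated score as written | Unrelated score with item 1 reversed |
|---|---|---|---|
| A. All five related items; not U2, not U3 | 5/5, *definitely related* | 1+0+0 = 1/3, *unlikely related* | 0+0+0 = 0/3, no grade |
| B. Time link and known effect only | 2/5, *possibly related* | 1+0+0 = 1/3, *unlikely related* | 0+0+0 = 0/3, no grade |
| C. No time link; cannot be caused; explained otherwise; no related item | 0/5, no grade | 0+1+1 = 2/3 | 1+1+1 = 3/3, *definitely unrelated* |
| D. Time link; cannot be caused; explained otherwise; no other related item | 1/5, no grade | 1+1+1 = 3/3, *definitely unrelated* | 0+1+1 = 2/3 |
| E. Time link and known effect; disease progression also explains it | 2/5, *possibly related* | 1+0+1 = 2/3 | 0+0+1 = 1/3, *unlikely related* |

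**Results.**

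1. Events A and B receive a grade from each list, and the two grades disagree. The cause is the shared item: reversing it removes the unrelated grade in both.
2. Without a time link the highest unrelated score is 0+1+1 = 2. *Definitely unrelated* needs 3, so only an event with a time link (such as D) can reach it. Reversing the item makes C, and not D, *definitely unrelated*.
3. The thresholds are bare numbers. Read as exact counts, related scores of 3 or 4 and an unrelated score of 2 have no grade, so C as written has none at all. Read as at least two and at least one, those scores are covered and C is *unlikely related*. A and B conflict under either reading.
4. Event E still meets both lists after the reversal (2/5 and 1/3). The duplicated sentence is not the only route to a double grade.

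**Does another passage settle it?** The pooling sentence acts on a grade already given. The SAP rule for a missing relationship covers missing grades, not conflicting ones. Protocol 13.1.4 gives the Clinical Events Committee a review for consistent criteria, but it does not name relatedness or rank the lists.

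**The case against.** The strongest defence is that the lists are aids. Protocol 10.1.2 rests the grade on timing and the investigator's clinical judgement, and the SAP agrees: "the investigator will evaluate the possible association between adverse events and study device/procedure according to the time relationship and its clinical judgment". A clinician facing event A would record one grade, almost certainly *definitely related*. Event A is also largely theoretical, because relief on stopping and return on reuse hardly apply to a catheter used in one procedure. All of this stands as a limit on the practical harm. It does not rescue the text: the Protocol sets numerical thresholds for its categories, and event B, which needs neither of those two items, shows the same conflict.

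Three stronger readings are tempting, and the documents support none of them.

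- *A reader might infer that the safety comparisons are distorted.* SAP 2.3.6.1 compares SAEs and complications without splitting by relatedness and summarises both by MedDRA class and term. Protocol 7.2 likewise says "Any reported SAE or discontinuation of assigned treatment due to an SAE will be classified using MedDRA". SAP 2.1.3.1 defines peri-procedural complications by period and type and only then grades them. Protocol 10.1.3 limits recording to SAEs and procedure-related complications, but does not say that the 10.1.2 grade decides entry.
- *A reader might infer that the lack of an order between the lists is an error of the same weight.* It is mostly missing detail, since judgement ends in one grade and the SAP offers *unable to determine*.
- *A reader might infer that the related list should prevail, by analogy with the SAP's missing-relationship rule.* That rule concerns absent judgements. With item 1 reversed, an event with no time link, of a kind the device cannot cause and explained otherwise, but which eased on stopping and returned on reuse, would score 3/3 unrelated and 2/5 related. Such a precedence would call it related.

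**Conclusion.** Unrelated item 1 is wrong as written. By the stated thresholds, a time link supports an unrelated grade, a 5/5 related event also qualifies as *unlikely related*, and *definitely unrelated* is closed to events with no time link. This follows from the text under either reading of the thresholds. That a negation was lost is an inference, though a likely one. A word lost in reading the PDF is an unlikely cause, because the verb stands in its un-negated form.

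The reach is small. It covers the related/unrelated status of SAEs and complications and nothing in the primary mRS analysis. The SAP names no table by relatedness, although its mention of a classification of SAEs and its rule for missing relationships suggest that the status may be reported. I give no size beyond the scores above: a tally of item combinations would depend on which ones are assumed possible and would not be an event rate. The correction is worth making, but the trial's conclusions do not depend on it.

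**What to change.** 1. In Protocol 10.1.2, reword unrelated item 1 so that it describes the absence of a fair temporal sequence.
2. Write the lower thresholds as *two or more* (possibly related) and *one or more* (unlikely related).
3. Reconcile the Protocol's four grades with the SAP's five, so that *unable to determine* is either in both documents or in neither.
4. As a minor clarification, the sponsor may say how an event meeting both lists, such as event E, is graded. I propose no particular precedence.

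The cost is a short amendment, which needs Ethics Committee approval before use (Protocol 11.1), and notice to the sites. If grades already recorded are re-checked, this should be done without knowledge of allocation where possible, because treating physicians are unblinded (Protocol 6.1.5). The re-check may be extra work, since Protocol 13.1.4 does not say that the Clinical Events Committee reviews relatedness. The SAP contains no item counts, so only its list of grades might need to change.
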